8.1.7 Primary Analysis

The following analyses for primary endpoints will be performed for three vaccine lots for all four vaccine strains.

- The adjusted GMT ratios (Day 21) and the corresponding two sided 95 % CI for each pairwise comparison of the lots will be calculated using ANCOVA models to assess if the two-sided 95 % CI limit falls between 0.67 and 1.5 for all four strains.

Statistical Analysis Plan

Hypotheses:

H0 : The lower bound of the 95 % CI is less than or equal to 0.67, or the upper bound of the 95 % CI is greater than or equal to 1.5.

H1 : The lower bound of the 95 % CI is greater than 0.67 and the upper bound of the 95 % CI is less than 1.5 for all pairwise combinations of lots and for each strain.

Multiplicity:

For multiplicity of hypothesis tests, a stepwise closed testing approach will be applied. The stepwise closed testing procedure (1.A/California: lot 1/lot 2 → lot 1/lot 3 → lot 2/lot 3 → 2.A/Hong Kong:lot 1/lot 2.... → 3.B/Brisbane... → 4.B/Phuket) will be stopped as soon as the first non-rejection of null hypothesis (H0).

8.2 SECONDARY IMMUNOGENICITY ENDPOINT(S) AND ANALYSES**8.2.1 Data Sets Analyzed**

Immunogenicity analysis (GMTs, GMFRs, SC rates, and SP rates) will be based on the PP set, and repeated using the FAS as the sensitivity analysis.

8.2.2 Measurements

Immunogenicity will be evaluated by measuring the serum antibody response induced in subjects, using the HI test against the homologous vaccine strains. HI antibody response will be measured using titer values.

The homologous influenza strains are listed in Section 8.1.2.

8.2.3 Scheduled Collection

Immunogenicity data will be collected on Days 0 and 21.

8.2.4 Derived and Imputed Data

- For the purpose of endpoints calculation, all HI antibody responses below the lower limit of quantitation (BLQ, <10) will be attributed a value of 5.
- GMT and 95% confidence intervals for the vaccine lots are calculated as the antilog of the mean and 95% confidence limits of log (base 10) transformed total titer values.
- GMFR is the geometric mean of the ratio of GMTs (Day 21/Day 0).

Statistical Analysis Plan

- SC rate is the proportion of subjects with either a ≥ 4 -fold increase in reciprocal HI titers between Day 0 and Day 21 or a rise of undetectable HI titer (i.e. <10) pre-vaccination (Day 0) to an HI titer of ≥ 40 on Day 21 post-vaccination.
- SP rate is the proportion of subjects attaining a reciprocal HI titer of ≥ 40 on Day 21 post-vaccination (the percentage of vaccine recipients with a serum HI titer of at least 1:40 following vaccination).

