4.2 SECONDARY IMMUNOGENICITY ENDPOINTS

HI antibody response induced by the Quadrivalent VLP Influenza Vaccine (pooled data from the three lots) against the homologous influenza strains on Days 0 and 21; HI antibody titers will be analyzed as follows:

- Seroconversion (SC) rate: the proportion of subjects with either a \geq 4-fold increase in reciprocal HI titers between Day 0 and Day 21 or a rise of undetectable HI titer (i.e. < 10) pre-vaccination (Day 0) to an HI titer of \geq 40 on Day 21;
- Seroprotection (SP) rate: the proportion of subjects attaining a reciprocal HI titer of \geq 40 on Day 21 (the percentage of vaccine recipients with a serum HI titer of at least 1:40 following vaccination);
- GMFR: geometric mean of the ratio of GMTs (Day 21/Day 0).

The immunogenicity endpoints for all four homologous influenza antigens will be evaluated according to the Center for Biologics Evaluation and Research (CBER) criteria for SC rate and SP rate.

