8.2.6 Model Fitting

The GMT will be derived by using Analysis of Variance (ANOVA) with vaccine lot as main effect. The log (base 10) transformed titer will be used and the back-transformation for mean GMT will be calculated with two-sided 95% confidence limits, based on the ANOVA model. The model is shown below:

```

Proc mixed data=ADZ (with the appropriate pooled subset);
  class trtpn;
  model aval= trtpn;
  Lsmeans trtpn/ cl alpha=0.05;
  Ods output LSMEANS=_outmix;
  run;
  Quit;
  Data outmix;
  Set outmix;
  GMT= 10**(Estimate);
  GMT_LCL = 10** (Lower);
  GMT_UCL = 10** (Upper);
  Run;

```

where *aval* is the \log_{10} transformed titer values.

For the SC and SP rates, the exact 95 % CI will be calculated using the following SAS® Code.

```

Proc freq data=ADZ (with the appropriate pooled subset);

```

Statistical Analysis Plan

```
by trtpn;  
table SC/out=_CNT binomial; *SC or SP  
exact binomial;  
ods output binomialprop=bin (where=(name1 in ('XL_BIN', 'XU_BIN')));  
run;
```

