8.2.7 Secondary Analysis

- The GMTs, GMFRs, and SC and SP rates of HI antibody will be calculated for the combined vaccine lots (overall), using descriptive statistics and 95 % CI; GMTs will also be summarized for each vaccine lot.
- The GMTs for HI antibody for each individual vaccine lot will be derived using ANOVA model with vaccine lot as main effect.
- For the SC and SP rates, the point estimates and the corresponding exact two-sided 95 % CIs will be calculated for the combined lots (overall) to assess whether the CI meets the CBER criteria.

Statistical Analysis Plan

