16. INDEX OF LISTINGS

ICH Section	Section Title
16.2.1.1	Subject Disposition
16.2.1.2	Subject Withdrawal
16.2.1.3	Not Randomized and Screening Failure Subjects (Failed Inclusion/Exclusion Criteria)
16.2.2.1	Protocol Deviations
16.2.3.1	Subject Visit
16.2.3.2	Analysis Populations
16.2.4.1	Demographics
16.2.4.2	Medical History
16.2.4.3.1	Prior Medications
16.2.4.3.2	Concomitant Medications
16.2.5	Vaccine Administration
16.2.6	Hemagglutination Inhibition (HI) Serology
16.2.7.1	Solicited Local and Systemic Reactions Days 0 to 7
16.2.7.2	Unsolicited Adverse Events
16.2.7.3	Serious Treatment-emergent Adverse Events
16.2.7.4	New Onset of Chronic Disease
16.2.7.5	Hypersensitivity Events
16.2.8.1	Pregnancy Test Results
16.2.8.2	Vital Signs
16.2.8.3	Physical Examinations

1009513

MEDICAGO R&D Inc.

CP-PRO-QVLP-011

Final version 1.0, 24JAN2018

Statistical Analysis Plan

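### Setting titers below 10 to 5 makes a rise from <10 to 20 count as seroconversion and leaves the separate <10-to-≥40 criterion with nothing to do

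*SAP*

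**What the plan says.** SAP Section 8.2.4 gives the derivation rules for the secondary immunogenicity endpoints. Its first bullet says that, in calculating endpoints, "all HI antibody responses below the lower limit of quantitation (BLQ, <10) will be attributed a value of 5". SC is one of those endpoints and is defined further down the same list. No bullet exempts it from the substitution.

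The SC bullet joins two criteria by either/or. One is an at least 4-fold "increase in reciprocal HI titers between Day 0 and Day 21 or a rise of undetectable HI titer". The other takes a subject from undetectable, given as <10, on Day 0 to at least 40 on Day 21. SAP Section 4.2 ("4-fold increase in reciprocal HI titers between Day 0 and Day 21 or a rise of undetectable HI titer") and protocol Section 10.2.2.2 carry the same two criteria. None of the three places limits the fold-rise criterion to a detectable baseline or sets a minimum Day 21 titer for it. Protocol Section 10.2.2.2 and SAP Section 4.2 assign no number to a titer of <10; the number comes from the substitution rule in SAP Section 8 (8.1.4 and 8.2.4).

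The code in SAP Section 8.2.6 ("table SC/out=_CNT binomial") tabulates an SC variable that has already been derived, so it does not settle how SC is obtained. Under SAP Section 8.2.7, point estimates and exact two-sided 95% CIs for the SC and seroprotection rates "will be calculated for the combined lots (overall) to assess whether the CI meets the CBER criteria".

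**The concern.** A separate criterion for subjects with an undetectable baseline has a purpose only if those subjects must reach 40 to count. Once <10 becomes 5 in every endpoint calculation, the fold-rise criterion can be computed for them too, and it is met at a Day 21 titer of 20. The stricter criterion is then bypassed.

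Two things are at stake. First, the error has one direction: the literal rule can add seroconverters but never remove any, so it can only raise the SC rate and its lower confidence limit, which is the figure read against a regulatory criterion for each strain. Second, two competent programmers could report different SC rates from the same titers. One would apply the substitution first; the other would treat the ≥40 criterion as the rule for undetectable baselines. The plan does not say which is right.

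**Working it through.** The plan states no figure to reproduce here, so the check is of the rule itself.

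**Inputs**
- Value for titers <10: 5 (SAP 8.2.4).
- Criterion 1: Day 21/Day 0 ≥ 4, with no minimum baseline (SAP 8.2.4 and 4.2; protocol 10.2.2.2).
- Criterion 2: Day 0 <10 and Day 21 ≥ 40 (same places).
- Per-protocol size: 1,200 less the assumed 10% = 1,080 (SAP 3.5), used only to illustrate size.

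**Ratios for an undetectable baseline**
- <10 to 20: 20/5 = 4.0. Criterion 1 is met with a Day 21 titer below 40.
- <10 to 40: 40/5 = 8.0. Criterion 1 is met with room to spare.
- For any Day 21 titer ≥ 40, Day 21/5 ≥ 8. Criterion 2 is therefore always contained in criterion 1, whatever the titer scale.
- The value 5 is what does this: with 10 substituted instead, <10 to 20 would be 2-fold and <10 to 40 exactly 4-fold.

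**Enumeration.** Assume a doubling-dilution scale (<10, 10, 20, …, 1,280), which gives 9 × 9 = 81 Day 0/Day 21 pairs.
- Pairs meeting criterion 1 or criterion 2: 28.
- Pairs meeting criterion 1 alone as the rule: the same 28.
- Pairs qualifying only through criterion 2: 0.
- Pairs qualifying if criterion 1 is limited to Day 0 ≥ 10: 27. The one pair lost is <10 to 20.

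If intermediate titers can occur (an assumption, for example from averaged duplicates), <10 to 28.3 is also affected. In general the affected subjects are those with Day 0 <10 and Day 21 from 20 to below 40.

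**Size.** Overstatement of the SC rate = P(Day 0 <10) × P(20 ≤ Day 21 < 40 given Day 0 <10). The documents give neither probability. Assuming 10–50% for the first and 5–30% for the second:

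| P(Day 0 <10) | P(20 to <40 given <10) | Overstatement (points) | Of 1,080 |
|---|---|---|---|
| 10% | 5% | 0.5 | 5.4 |
| 20% | 15% | 3.0 | 32.4 |
| 30% | 20% | 6.0 | 64.8 |
| 50% | 30% | 15.0 | 162 |

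Every affected subject has a Day 21 titer below 40, so the overstatement cannot exceed 1 minus the seroprotection rate. The 15-point case would therefore need a seroprotection rate of 85% or less.

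**Against sampling error.** Exact 95% CIs at n = 1,080:
- 540 (50.0%): 47.0–53.0, half-width 3.0 points.
- 756 (70.0%): 67.2–72.7, half-width about 2.8 points.

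Starting from an assumed true-rule SC rate of 60.0% (648; CI 57.0–62.9):
- +0.5 points: 653, 60.5% (57.5–63.4).
- +6 points: 713, 66.0% (63.1–68.8).
- +15 points: 810, 75.0% (72.3–77.6).

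The shift passes the CI half-width only when the product of the two probabilities is above about 3%, for example 20% × 15%.

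**The case against.** The strongest reply is that this is redundancy, not contradiction. The criteria are joined by either/or, both can be applied together, and one simply adds nothing. A reader can also infer the intent: the second criterion is worded by status (undetectable) rather than by the number 5, it appears identically in three places, and a specific rule would normally be taken to govern over a general substitution. SAP Section 13 provides for a programming and quality-control plan, which makes silent divergence less likely. The effect falls on one secondary rate outside the formal hypotheses and multiplicity procedure, the CBER thresholds are not in the documents, and the size rests wholly on assumed inputs.

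Much of this stands. The bullets are not logically incompatible, the intended reading is probably the stricter one, and neither the size nor a changed CBER result can be shown.

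It does not remove the problem. The inferred intent is nowhere written, and the written rule gives the opposite answer for <10 to 20. A quality-control plan can check only against a stated rule, and independent programmers could agree on the unintended reading. The point does not need a known size: a written rule that disables one of the protocol's two SC criteria, and can err only in the favourable direction, should be corrected before results are seen.

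**Conclusion.** The concern holds. As written, SAP Section 8.2.4 counts <10 to 20 as seroconversion and makes the <10-to-≥40 criterion inoperative. This follows from the text by arithmetic and needs no assumption about the data.

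The size is undeterminable from the documents. The 0.5 to 15 points rest on assumed baseline and response distributions, with 1 minus the seroprotection rate as a firm ceiling. At the low end the effect would be lost in sampling error; above about 3 points it would not. The reach is limited to the pooled SC rate and its comparison with the CBER criteria. The lot-to-lot GMT ratios, seroprotection rate, GMFR and safety analyses do not use the SC definition. It should be fixed, but it does not threaten the trial's primary conclusion.

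**What to change.** In SAP Section 8.2.4, repeated in Section 4.2, define SC as:

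(Day 0 ≥ 10 and Day 21/Day 0 ≥ 4) or (Day 0 <10 and Day 21 ≥ 40).

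Add that the value 5 is used for GMT, GMT ratio and GMFR, but not to compute the fold rise for SC. This gives both criteria their function again. It needs no protocol amendment, because protocol Section 10.2.2.2 assigns no value to <10. SAP Section 11 reports no changes from the protocol, so a line there recording this as a clarification would avoid later questions.

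If the sponsor does intend <10 to 20 to count, the SAP should say so and drop the idle criterion; because the protocol states that criterion too, the change would then belong in Section 11. Either way the rule should be fixed before unblinding.

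The cost is one clause and one line of derivation code. No new data are needed, since individual titers are already to be listed (Listing 16.2.6, "Hemagglutination Inhibition (HI) Serology"). The downside for the sponsor is that the reported SC rate may be less favourable, by an amount that cannot be known in advance.

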8.2.5 Data Summarization

The immunogenicity parameters will be summarized by the vaccine lots and by homologous influenza strains. Descriptive statistics and 95% CIs will be calculated for the immunological parameters.

8.2.6 Model Fitting

The GMT will be derived by using Analysis of Variance (ANOVA) with vaccine lot as main effect. The log (base 10) transformed titer will be used and the back-transformation for mean GMT will be calculated with two-sided 95% confidence limits, based on the ANOVA model. The model is shown below:

```

Proc mixed data=ADZ (with the appropriate pooled subset);
  class trtpn;
  model aval= trtpn;
  Lsmeans trtpn/ cl alpha=0.05;
  Ods output LSMEANS=_outmix;
  run;
  Quit;
  Data outmix;
  Set outmix;
  GMT= 10**(Estimate);
  GMT_LCL = 10** (Lower);
  GMT_UCL = 10** (Upper);
  Run;

```

where *aval* is the \log_{10} transformed titer values.

For the SC and SP rates, the exact 95 % CI will be calculated using the following SAS® Code.

```

Proc freq data=ADZ (with the appropriate pooled subset);

```

Statistical Analysis Plan

```
by trtpn;  
table SC/out=_CNT binomial; *SC or SP  
exact binomial;  
ods output binomialprop=bin (where=(name1 in ('XL_BIN', 'XU_BIN')));  
run;
```

8.2.7 Secondary Analysis

- The GMTs, GMFRs, and SC and SP rates of HI antibody will be calculated for the combined vaccine lots (overall), using descriptive statistics and 95 % CI; GMTs will also be summarized for each vaccine lot.
- The GMTs for HI antibody for each individual vaccine lot will be derived using ANOVA model with vaccine lot as main effect.
- For the SC and SP rates, the point estimates and the corresponding exact two-sided 95 % CIs will be calculated for the combined lots (overall) to assess whether the CI meets the CBER criteria.

Statistical Analysis Plan

9. SAFETY

The analysis population used for safety analyses will be the SAS. Safety and tolerability endpoints (solicited local and systemic reactions, AEs, and vital signs) will be tabulated.

9.1 REACTIONS AND ADVERSE EVENTS

All subjects in the SAS will be included in the AE analysis.

9.1.1 Measurements

Both solicited reactions and unsolicited AEs will be collected.

Solicited Local and Systemic Reactions

Subjects will be monitored for both solicited local reactions (erythema, swelling and pain at the injection site) and solicited systemic reactions (fever, headache, fatigue, muscle aches, joint aches, chills, a feeling of general discomfort, swelling in the axilla, and swelling in the neck).

The intensity of the solicited local and systemic reactions will be graded as: mild (1), moderate (2), severe (3), or potentially life threatening (4). Their causal relationship with the study vaccine will be assessed by the Investigator (definitely not related, probably not related, possibly related, probably related, or definitely related).

Unsolicited Adverse Events

An AE or adverse experience is defined as any untoward medical occurrence in a subject or clinical investigation subject who was administered a pharmaceutical product, with or without a causal relationship with the treatment. An AE can be any favorable and unintended sign, symptom, or disease temporally associated with the use of a medicinal product, whether or not related to a medicinal product.

A treatment-emergent AE (TEAE) is any AE that is new in onset or was aggravated in severity or frequency following the administration of study drug, up to and including the last visit of the study. Treatment emergence will be determined by comparing the AE start date/time with the actual date/time of vaccination. In the case that the AE start date/time are incomplete, treatment emergence will be imputed according to the algorithm in Section 6.3 of the SAP.

Each AE report contains a description of the AE, the date and time of onset and resolution,

Statistical Analysis Plan

intensity, whether it is serious, any required treatment or action taken, outcome, relationship to the investigational vaccine, and whether the AE caused withdrawal from the study. Data will be recorded on the CRF by the total span of time covered for each event, rather than by a separate record for each report of the same event.

The intensity of all AEs will be graded as mild (1), moderate (2) severe (3), or potentially life-threatening (4). Their causal relationship with the study vaccine will be assessed by the Investigator (definitely not related, probably not related, possibly related, probably related or definitely related).

Unsolicited AEs will be coded using MedDRA 20.0 and analyzed by PT and System Organ Class (SOC).

All AEs will be evaluated to determine whether they should be considered as an NOCD or an SAE. In the context of this study, all NOCDs that may plausibly have an allergic, autoimmune, or inflammatory component are to be reported. An SAE is considered to be any untoward medical occurrence (whether or not considered to be related to the study vaccine) that, at any dose results in death; is life-threatening (at the time of the event); requires inpatient hospitalization (≥ 24 hours) or prolongation of existing hospitalization (elective hospitalizations/procedures for pre-existing conditions that have not worsened are excluded); results in persistent or significant disability/incapacity; is a congenital abnormality/birth defect; or is another medically important event (e.g. any cases of newly diagnosed cancer).

Hypersensitivity cases will be identified using a standardized MedDRA query (SMQ) for hypersensitivity.

9.1.2 Collection Schedule

Solicited local and systemic reactions will be collected from the time of vaccination through Day 7. Any solicited local or systemic reactions lasting beyond Day 7 will be considered an AE with a start date 8 days post-vaccination.

Solicited local and systemic reactions occurring within 15 minutes post vaccination will be considered as Immediate Complaints.

All AEs occurring within 21 days after vaccination will be recorded in the source documents or MA and reported in the “Adverse Event” form in the subject’s eCRF, irrespective of intensity or whether or not they are considered to be vaccination-related.

The SAEs and NOCDs will be followed up until complete resolution or stabilization.

Statistical Analysis Plan

Follow-up of unresolved SAEs, AEs leading to withdrawal, or NOCDs after the end of the study period will continue under the discretion of the Investigator.

9.1.3 Derived and Imputed Data

Every attempt will be made to get complete dates and times or best estimates for AEs which may occur or start outside of the clinic. AEs which begin during the subject's stay in clinic are expected to have complete dates and times. Incomplete AE dates and times will not be imputed.

There is no imputation in cases where severity or relationship information is missing for TEAEs.

Days from vaccination are calculated as date of event – date of vaccine +1.

9.1.4 Data Summarization

Immediate complaints, solicited local and systemic reactions, and AEs will be summarized according to the vaccine lot and overall.

Additional summaries will be provided for each vaccine lot and overall by severity and by relationship. The local and systemic signs and symptoms tabulations will also include the immediate complaints. The proportion of subjects with a non-zero grade will be included.

9.1.5 Model Fitting

No inferential tests will be used on these data.

9.1.6 Data Presentation

Displays of AEs by vaccine lot and overall will include:

- Overall Summary of Solicited Reactions and Unsolicited TEAEs
This table will include the number and percentage of subjects who had solicited reactions or unsolicited TEAEs, who had immediate complaints, solicited local and systemic reactions, who had \geq severe reactions and events, who had serious events, and who were withdrawn due to an AE or who died.

The following summaries of immediate complaints (solicited local and systemic reactions occurring 15 minutes post vaccination) will be presented by vaccine lot and overall:

- Summary of incidence of immediate complaints.

Statistical Analysis Plan

- Summary of immediate complaints by symptom and maximum intensity (mild, moderate, severe, or potentially life-threatening).
- Summary of immediate complaints by symptom and relationship to vaccination (related or not related). The “related” category will include the Investigator causal assessments of definitely related, probably related, and possibly related; the “not related” category will include the Investigator causal assessments of probably not related and definitely not related.

The following summaries of solicited reactions will be presented by vaccine lot and overall:

- Summary of incidence of solicited reactions by symptom.
- Summary of solicited reactions by symptom and maximum severity (mild, moderate, severe, or potentially life-threatening). The “related” category will include the Investigator causal assessments of definitely related, probably related, and possibly related; the “not related” category will include the Investigator causal assessments of probably not related and definitely not related.
- Summary of solicited reactions by symptom and relationship to study vaccine (related or not related).
- Summary of severe and potentially life-threatening related solicited reactions

The following summaries of unsolicited TEAEs will be presented by vaccine lot and overall:

- Summary by MedDRA SOC and PT.
- Summary by severity (mild, moderate, severe, or potentially life-threatening), MedDRA SOC, and PT.
- Summary by relationship to study vaccine (related or not related), MedDRA SOC, and PT. The “related” category will include the Investigator causal assessments of definitely related, probably related, and possibly related; the “not related” category will include the Investigator causal assessments of probably not related and definitely not related.
- Summary of severe and potentially life-threatening related TEAEs by MedDRA SOC and PT.
- Summary of serious TEAEs by MedDRA SOC and PT.
- Summary of NOCDs by SOC and PT.

Statistical Analysis Plan

The following summary of hypersensitivity events will be presented by vaccine lot and overall:

- Summary by MedDRA SOC and PT.

AEs will be listed by subject, treatment (lot) and day of onset for all AEs. Solicited reactions including Immediate Complaints will be displayed in Listing 16.2.7.1. Unsolicited AEs will be listed in Listing 16.2.7.2, NOCDs will be listed in Listing 16.2.7.4, and hypersensitivity will be listed in Listing 16.2.7.5.

